### 3. DESCRIPTION OF DESIGN AND TRIAL POPULATION

#### 3.1 OVERALL TRIAL DESIGN AND PLAN

This is a 12-week, multi-center, randomized, double-blind, double dummy placebo controlled, parallel group study in patients with prodromal AD.

In total, 288 patients with prodromal AD who meet the entry criteria are planned to be randomized in this trial. The randomized treatment will be double blind. Each patient will receive active treatment with BI 409306 (each patient will receive one active treatment and placebos to match the alternative active treatment) or placebos (each patient will receive placebos to match each of the active treatments).

After obtaining informed consent, patients will undergo a screening period of a maximum of 5 weeks. All patients who successfully complete the screening period and are eligible for the study, then enter a minimum of 2 weeks of single blinded placebo run-in before randomization.

Patients who successfully complete the single-blinded phase and who fulfil both the inclusion and exclusion criteria will be randomized to the 12-week double blind treatment period at visit 3 and will be assigned to one of the 5 treatment groups namely: once daily (QD) 10 mg, 25 mg, or 50 mg BI 409306, or 25 mg BI 409306 twice daily (BID), or placebo.

[figure not shown]

Figure 3.1:1 Study design

After the end of the double-blind treatment period, patients will be followed up for an additional 4 weeks without study medication. Patients will be evaluated for efficacy at randomization, at visit 5 (week 4) and at visit EOT (week 12). Safety will be formally evaluated at each visit until end of the observational period which is 28 days after end of treatment or for an appropriately longer time in case of unresolved adverse events.

Adverse events will be collected throughout the trial according to [section 5.2.2.2](#).

Proprietary confidential information.

© 2017 Boehringer Ingelheim International GmbH or one or more of its affiliated companies. All rights reserved.

This document may not - in full or in part - be passed on, reproduced, published or otherwise used without prior written permission.

### 3.1.1 Administrative structure of the trial

The trial is sponsored by Boehringer Ingelheim (BI). Boehringer Ingelheim will appoint a Trial Clinical Monitor (TCM), responsible for coordinating the activities required in order to manage the trial in accordance with applicable regulations and internal Standard Operating Procedures (SOPs), directing the clinical trial team in the preparation, conduct and reporting of the trial, order the materials as needed for the trial, ensures appropriate training and information of local clinical monitors (CMLs), CRAs and investigators in participating countries.

Data management and statistical evaluation will be done by BI according to BI SOPs. For these activities, a Trial Data Manager and a Trial Statistician will be appointed. Tasks and functions assigned in order to organize, manage, and evaluate the trial will be defined according to BI SOPs. A list of responsible persons will be given in the Clinical Trial Master File (CTMF) document.

[REDACTED] has been selected as a service provider to support the following tasks related to the neuropsychological assessments: rater prequalification, rater training (online and at investigator meeting), provision of rater materials and central review of assessments (see [section 5.1.2](#) and [section 8.2](#) for details).

A central laboratory and central ECG service vendor will be used for this trial. The organization of the trial in the participating countries will be done by the respective local BI organization (OPU) or by a Contract Research organization (CRO) with which the responsibilities and tasks have been agreed and a written contract has been filed before initiation of the clinical trial. In each local BI-organisation (OPU) participating in this study, a local clinical monitor (CML) will be appointed who will be responsible for coordinating the activities required in order to manage the trial in accordance with applicable regulations and internal SOPs in the countries covered by the respective BI OPU.

A Coordinating Investigator will be nominated to coordinate investigators at different sites participating in this multi-centre trial. Tasks and responsibilities for the Coordinating Investigator will be defined in a contract filed before initiation of the trial. Documents on participating (Principal) investigators and other important participants as defined in the monitoring manual, especially their curricula vitae, will be filed in the CTMF.

The Investigator Site File (ISF) will be kept at the sites as far as required by local regulations and BI SOPs. A copy of the ISF documents will be kept as an electronic Clinical Trial Master File.

## 3.2 DISCUSSION OF TRIAL DESIGN, INCLUDING THE CHOICE OF CONTROL GROUP(S)

All patients who successfully complete screening and are eligible for the study will undergo a single blinded placebo run-in phase in order to generally familiarize with the clinical setup of the neuropsychological tests as well as the regular intake of study drug to ensure compliance with study procedures.

Proprietary confidential information.

© 2017 Boehringer Ingelheim International GmbH or one or more of its affiliated companies. All rights reserved.

This document may not - in full or in part - be passed on, reproduced, published or otherwise used without prior written permission.

A parallel group design is the appropriate design as the inherent within-patient variability and the progressive nature of the disease makes it difficult if not impossible to employ a cross-over design.

To assess a comparative benefit/risk ratio treatment BI 409306 patients will randomly be allocated to one of 4 active doses or placebo only in a 1:1:1:1:2 ratio (for rationale of allocation of treatments refer to [section 7.1](#) and for justification of doses refer to [section 4.1.3](#)).

In order to estimate the absolute drug effect on cognition and function, a double-blind comparison against placebo is included in this trial. With this approach we follow the EMA guideline on medical products for the treatment of Alzheimer's disease and other dementias (CPMP/EWP/553/95 Rev. 1, 2008).

The current standard treatment of cognitive and functional impairment in AD shows substantial treatment effects during the first three months of treatment. Therefore, a 12-week treatment period is considered to also be sufficient to assess the efficacy, safety and tolerability of BI 409306 in prodromal stages of this disease.

The data collected in this double-blind, randomized, placebo-controlled trial are standard in diagnosed Alzheimer's disease and therefore regarded to also provide important information in terms of efficacy, safety and tolerability on the use of BI 409306 maintenance treatment in patients with prodromal AD.

### 3.3 SELECTION OF TRIAL POPULATION

About 1000 patients will be screened for the study in approximately 12 countries. About 60 study centres will be participating to ensure approximately 288 patients are randomised to study treatment.

Recruitment will be competitive and participating sites are expected to randomize at least 288 patients. Patients who fail to complete all assessments in terms of primary and secondary endpoints according to the study protocol will not be considered study completers (see [section 6.2](#) and [section 7.3](#) for details). Patients who discontinue following randomization may not be re-enrolled at a later date. A record is kept of all patients failing to complete all trial visits and their reasons for discontinuation.

This trial (1289.5) investigates patients with cognitive impairment caused by the Alzheimer's disease. In parallel BI is investigating the effect of BI 409306 in patients with mild Alzheimer's dementia in the study 1289.7. It is expected that both trials share a high percentage of trial sites. The Mini Mental Stage Examination (MMSE) evaluates the severity of cognitive impairment and this assessment is used in both trials as part of the eligibility assessments with the following requirements:

1. 1289.5 – MMSE score  $\geq 24$
2. 1289.7 – MMSE score  $\geq 18 - 26$

Proprietary confidential information.

© 2017 Boehringer Ingelheim International GmbH or one or more of its affiliated companies. All rights reserved.

This document may not - in full or in part - be passed on, reproduced, published or otherwise used without prior written permission.

Patients who do not reach the required scores of  $\geq 24$  in MMSE and CDR total score 0 or 0.5 are not eligible for this study and must be registered as screen failure in IRT. If the result of the MMSE and CDR fulfill the requirements of the parallel trial 1289.7 and the patient and his study partner agree to alternatively participate in 1289.7 after giving a new consent then the results of the MMSE and CDR can be transferred into the database of 1289.7 without repeated performance of the MMSE and CDR and vice versa. This prevents the risk of unwanted learning effects which would be a consequence of repeating the MMSE and CDR in the same patient. This rule only applies if the screening visit for 1289.7 is no later than 7 days after the MMSE/CDR for 1289.5 was performed. The patient will then be registered as a new patient in the IRT of 1289.7. This does not apply to sites participating in only one of the 1289.5/1289.7 studies.

Permission to randomize more than 15 patients per site must be obtained in writing from the TCM at Boehringer Ingelheim. This will only be allowed after a careful review of the enrolment status.

Re-screening of not yet randomised patients can be allowed in exceptional cases but should be discussed on a case-by-case basis between the study site, Monitor staff and with the TCM.

A log of all patients included into the study (i.e. having given informed consent) will be maintained in the ISF at the investigational site irrespective of whether they have been treated with investigational drug or not.

### 3.3.1 Main diagnosis for study entry

Patients with diagnosis of prodromal AD in accordance with the recommendation of the International Working Group (IWG), Dubois et al. 2014) [[R14-2556](#)]):

- Symptoms noticed by the patients or informant
- Cognitive testing confirming prodromal symptoms
- Biomarker evidence of AD pathology
- No evidence of other forms of dementia
- No other concomitant illness or medication which could confound or prohibit completion in the trial by the patient

### 3.3.2 Inclusion criteria

Patients will be included in this study if they meet all of the following criteria:

1. Male and female patients with an age  $\geq 55$  years. Patients older than 85 years may be included based on an acceptable general health status, (e.g. concomitant diseases, physical capability to follow the required study procedures [visits etc.]) per investigators judgement.
2. Body weight  $\geq 50$  kgs.

Proprietary confidential information.

© 2017 Boehringer Ingelheim International GmbH or one or more of its affiliated companies. All rights reserved.

This document may not - in full or in part - be passed on, reproduced, published or otherwise used without prior written permission.

3. Patients with a confirmed diagnosis of prodromal AD on neuropsychological testing defined as:

- Mini-Mental State Examination (MMSE) score:  $\geq 24$   
and
- a global CDR-score of 0 or 0.5  
and
- Free and Cued Selective Recall Reminding Test (FCSRT) score:
  - free recall test:  $\leq 20$  (out of 48) and
  - total recall test:  $\leq 42$  (out of 48)

Patients who do not reach the required score in FCSRT will additionally perform the Wechsler Memory Visual Paired Associates test. If the Wechsler Memory Visual Paired Associates test shows a cognitive deficit worse than 1 standard deviation to the mean (compared to the reference values of age and educational norms for inclusion), then the patients can be considered to be eligible for the study. [\[R14-4676\]](#)

4. Confirmation of abnormal markers of AD pathology either via a), or alternatively b) mentioned below:\*

a) Presence in cerebrospinal fluid of (samples taken within past 4 months may be eligible, refer to [section 5.6.1](#) and [appendix 10.2](#) for full details):

- low A $\beta$ 1-42 concentrations ( $< 640$  pg/mL) and increased total tau concentrations ( $> 375$  pg/ml),

or / and

- low A $\beta$ 1-42 concentrations ( $< 640$  pg/mL) and increased phospho-tau concentrations ( $> 52$  pg/mL in cerebrospinal fluid),

or

b) Abnormal amyloid deposition in a cerebral PET scan. Scans performed in the past according to the recommendations in [section 5.3.2.1](#) are acceptable.

\* Note – CSF or PET could be the procedure of choice as per local regulations or IRBs/ IECs or site practices (as applicable).

5. Patients who have not received prescribed drugs for treatment of AD (including acetyl cholinesterase inhibitors (donepezil, galantamine, rivastigmine, tacrine, phenserine) and Memantine) within three months prior to screening.
6. Patients must have at least 6 years of formal education and fluency in the test language as verbally confirmed by the patient and documented by the study investigator.

Proprietary confidential information.

© 2017 Boehringer Ingelheim International GmbH or one or more of its affiliated companies. All rights reserved.

This document may not - in full or in part - be passed on, reproduced, published or otherwise used without prior written permission.

7. Patients must have given written informed consent in accordance with GCP and local legislation prior to any study procedures. All patients must be able to give informed consent personally and have capacity for such consent. An informed consent given by a legal representative will not be accepted.
8. Patients must have a reliable study partner (per investigator judgement, for instance a family member, partner etc., guardian). This person should be in close contact with the patient and agree to accompany the patient on all scheduled visits. The person should also agree to be reachable by phone and should be able to contribute to the neuropsychological assessments of the patient, wherever necessary. This person should be able to communicate in the language in which the patient is being assessed and should also serve as a back-up contact for the study site. This person must sign a separate informed consent form which describes their contribution during the study.

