#### Primary analysis model

The restricted maximum likelihood (REML) based mixed effects model with repeated measurements (MMRM) will be used for the change from baseline in NTB total score after 12 weeks of treatment. The model will include fixed, categorical effects of treatment, visit and treatment by visit interaction, as well as the continuous fixed covariates of baseline and baseline-by-visit interaction. Patient will be considered as random effect. The unstructured covariance structure will be used to model the within patient errors. If this analysis fails to converge, compound symmetry covariance structure might be used. The Kenward-Roger approximation will be used to estimate denominator degrees of freedom. Analyses will be implemented using SAS PROC MIXED. The primary treatment comparisons will be the contrast between treatments after 12 weeks of treatment. Adjusted mean values as well as treatment contrasts will be presented together with the 95 % confidence intervals.

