#### 7.6 DETERMINATION OF SAMPLE SIZE

The primary efficacy hypothesis will be tested by comparing the dose group of BI 409306 with the peak response in the fitted regression model to the placebo group on the primary

Proprietary confidential information.

© 2017 Boehringer Ingelheim International GmbH or one or more of its affiliated companies. All rights reserved.

This document may not - in full or in part - be passed on, reproduced, published or otherwise used without prior written permission.

endpoint, the change from baseline in NTB total score after 12-week treatment. (See [section 7.2](#) for the details of hypothesis testing.)

As previously mentioned, the randomization allocation ratio of 1:1:1:1:2 of 10 mg, 25 mg, 50 mg, 25 mg BID of BI 409306, and placebo is used so that 33 % of patients will be randomized to placebo. Since these results in an unequal allocation of treatment to placebo, the sample size required for the active treatment and placebo for various effect size are displayed separately. The sample size calculations in [Table 7.6:1](#) displays the range of effect sizes considered for this trial under these assumptions using a 2-sided alpha of 0.05 with 80 % power. The two-sample t-test method with unequal n's in nQuery Advisor 6.01 was used for the calculation.

Table 7.6: 1 Sample size calculations

Standardized effect size	0.45	0.50	0.55	0.6	0.65
Power	80%	80%	80%	80%	80%
n for each active treatment arm	59	48	40	34	29
n for placebo arm	118	96	80	68	58
Total	354	288	240	204	174

Based on the calculations provided in [Table 7.6:1](#), a sample size of 48 per active treatment arm and 96 for placebo arm was selected as adequate for a phase II proof of concept trial. This sample size would allow us to detect an effect size of 0.5 with 80 % power or an effect size of 0.6 with 92 % power, 2-sided alpha at 0.05.

*Assuming a 10% dropout rate, this sample size would allow us to detect an effect size of 0.53 with 80% power and assuming a 20% dropout rate, this sample size would allow us to detect an effect size of 0.56 with 80% power, 2-sided alpha at 0.05.*

Proprietary confidential information.

© 2017 Boehringer Ingelheim International GmbH or one or more of its affiliated companies. All rights reserved.  
This document may not - in full or in part - be passed on, reproduced, published or otherwise used without prior written permission.

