9 ADDITIONAL SECTIONS

9.1 CALCULATION OF NTB TOTAL SCORE

Below is a description for the NTB along with detail on deriving the scores for the total scores and several subscales. The derivations are based on [6] and the supplementary information from [7].

Table 9.1: 1 NTB description and scoring

The NTB is a cognitive assessment made up of the following 9 component tests:

1. Wechsler Memory Scale Visual Paired Associates—Immediate (WMVis-I), range 0 to 18;
2. Wechsler Memory Scale Verbal Paired Associates—Immediate (WMVer-I), range 0 to 24;
3. Rey Auditory Verbal Learning Test—Immediate (RAVL-I), range 0 to 105;
4. Wechsler Memory Scale—Digit Span (WMDS), range 0 to 24;
5. Controlled Word Association Test (COWAT);
6. Category Fluency Test (CFT);
7. Wechsler Memory Scale Visual Paired Associates—Delayed (WMVis-D), range 0 to 6;
8. Wechsler Memory Scale Verbal Paired Associates—Delayed (WMVer-D), range 0 to 8;
9. Rey Auditory Verbal Learning Test—Delayed (RAVL-D), range 0 to 30.

The first 3 tests assess immediate memory (WMVis-I, WMVer-I, RAVL-I), the second 3 assess executive function (WMDS, COWAT, CFT), and the last 3 assess delayed memory (WMVis-D, WMVer-D, RAVL-D). Higher scores indicate better cognition on all tests.

First, a total score for each component test except the RAVL-D is calculated by summing all the scores. For the RAVL-D, the total score is calculated as:

total part 7 + total part 8 correct + (15 - total part 8 incorrect).

Then, a z-score for each component test is calculated as follows. For each subject j , at assessment time point t (with $t = 0$ denoting baseline), let y_{ijt} denote subject j 's score at time t for the i th component test ($i = 1, \dots, 9$). Then the corresponding z-score, denoted z_{ijt} , is defined as:

$$z_{ijt} = (y_{ijt} - \bar{y}_{ij\theta}) / s_{ij\theta}$$

Proprietary confidential information © 2017 Boehringer Ingelheim International GmbH or one or more of its affiliated companies

Where y_{i0} and s_{i0} denote the average and the standard deviation of the baseline scores on the i th component test across all study subjects in the FAS.

Finally, the NTB total score z_{jt} for the j th subject at time t is calculated by averaging the 9 component test z-scores:

$$z_{ijt} = (z_{1jt} + \dots + z_{9jt})/9$$

The NTB total z-score will be calculated only if scores for at least 6 of the 9 component tests are not missing [6].

In addition, the following subscales are defined:

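### Optional efficiency gain: the primary NTB model could also adjust for pre-treatment ADAS-Cog11, which is already collected, for a gain of between about nil and 4 to 5 power points

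*Protocol*

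**What the plan says.** Protocol 7.3.1 specifies an MMRM with treatment, visit and their interaction, "as well as the continuous fixed covariates of baseline and baseline-by-visit interaction". Baseline is the NTB total z-score at Visit 3. SAP 7.4.1 refers back to this model, and the code in SAP 9.3 contains no other prognostic covariate. SAP 6.5 leaves centre and country out, and Protocol 7.5 says that randomization is not stratified.

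Other cognitive scores exist before treatment. Inclusion criterion 3 in Protocol 3.3.2 requires MMSE, a global CDR score and the "Free and Cued Selective Recall Reminding Test (FCSRT) score". The flow chart and Protocol 6.2.1 add ADAS-Cog11 at Visit 1, and Protocol 6.2.2 repeats it at Visit 3 alongside the NTB. By schedule, every randomized patient therefore has MMSE, FCSRT and two ADAS-Cog11 scores before the first dose of randomized treatment.

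Memory dominates the NTB. SAP 9.1 says "The first 3 tests assess immediate memory (WMVis-I, WMVer-I, RAVL-I"), and it assigns three more of the nine tests to delayed memory.

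In Protocol 7.6, "a sample size of 48 per active treatment arm and 96 for placebo arm was selected". The stated reason is that this would "detect an effect size of 0.5 with 80 % power or an effect size of 0.6 with 92 % power". The method is described as "The two-sample t-test method with unequal n's in nQuery Advisor 6.01 was used for the calculation".

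**The concern.** The baseline NTB comes from one occasion, and it is the first NTB in the schedule. It therefore carries measurement error, and the total may still be scored with up to three of the nine tests missing. Another pre-treatment measure of the same ability, especially one from a different day, can carry information on the Week 12 NTB that the baseline NTB does not.

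If so, adjusting for it shortens the standard error of every NTB contrast: pooled doses versus placebo (Step 1), the peak-response dose versus placebo (Step 3), and each dose versus placebo. With 48 patients per active arm, a free reduction in variance is worth considering. A pre-specified, pre-treatment covariate does not bias a randomized comparison.

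**Working it through.** **1. Reproduce the plan's figures.** Inputs from Protocol 7.6 are a standardized effect of 0.5, "using a 2-sided alpha of 0.05 with 80 % power", and 48 versus 96 patients. The allocation "is used so that 33 % of patients will be randomized to placebo", so one dose versus placebo is 1:2. For a two-sample t-test the noncentrality is d × √(n₁n₂/(n₁+n₂)) = 0.5 × √(48×96/144) = 0.5 × √32 = 2.83, on 142 degrees of freedom. Power is 80.2%; at d = 0.6 it is 92.1%. All five columns of Table 7.6:1 reproduce (active-arm n of 59, 48, 40, 34 and 29). The detectable effects under dropout also reproduce: 0.53 with 43 versus 86, and 0.56 with 38 versus 76.

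**2. Effect of an added covariate.** Let g be the share of the residual variance of Week 12 NTB, after baseline NTB, that the added score explains. The standard error is multiplied by √(1−g) and the effective effect size becomes 0.5/√(1−g). This treats 0.5 as the effect size under the planned model; the protocol does not say which SD was used. The equivalent number of extra patients is 288/(1−g) − 288.

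| g | Effective d | Power, 48 vs 96 | Equivalent extra patients |
|---|---|---|---|
| 0 | 0.500 | 80.2% | 0 |
| 0.02 | 0.505 | 81.0% | 6 |
| 0.05 | 0.513 | 82.2% | 15 |
| 0.10 | 0.527 | 84.2% | 32 |
| 0.117 | 0.532 | 84.8% | 38 |

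For scale, g = 0.10 would bring the detectable effect under 10% dropout back to 0.527 × √0.90 = 0.50.

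**3. Plausible g (assumptions; the documents give no correlations).** Take Y₀ = T + e₀ and Y₁₂ = T + D + e₁, with a covariate that has correlation R with T. The residual variance is 1/(1/vT + 1/ve + 1/(vT(1/R²−1))) + vD + ve, compared with the same expression without the third term.

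- Upper corner: retest correlation 0.80, all unshared variance noise, R = 0.8, so vT = 0.80, ve = 0.20, vD = 0. Without the covariate: 1/(1.25+5) + 0.20 = 0.360. With it: 1/(1.25+5+2.222) + 0.20 = 0.318. Hence g = 11.7%.
- Lower corner: retest correlation 0.90, 75% of unshared variance noise, R = 0.6, so vT = 0.90, ve = 0.075, vD = 0.025. Without: 1/(1.111+13.333) + 0.10 = 0.1692. With: 1/(1.111+13.333+0.625) + 0.10 = 0.1664. Hence g = 1.7% and power is 80.9%.

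**4. Less favourable assumptions, same formula.**
- R = 0.4: g is 0.6% to 1.6% over the same other ranges.
- Half of the unshared variance noise, retest 0.90, R = 0.6: g = 0.9%.
- Error correlation of 0.2 between the covariate and baseline NTB: the upper corner falls from 11.7% to 6.8%, and the lower corner falls to about zero.

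**5. One score alone.** Now set vT = 1, and let NTB reliability run from 0.70 to 0.95, the score's correlation with true cognition from 0.3 to 0.7, and true-change variance from 0.05 to 0.10. With independent errors, g runs from 0.1% to 8.6%, so power runs from about 80.3% to 83.6%. A middle case has reliability 0.80, correlation 0.5 and change variance 0.05. Residual variance goes from 1/5 + 0.30 = 0.500 to 1/5.333 + 0.30 = 0.4875, so g = 2.5% and power is 81.2%.

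**6. Cost of estimation.** With residual degrees of freedom of about N − 7, one covariate breaks even at g = 1/281 = 0.4% (N = 288) or 1/223 = 0.4% (N = 230, the 20% dropout case). Three covariates need 3/281 = 1.1% or 3/223 = 1.3%.

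**The case against.** The strongest reply is that nothing here is wrong. Randomization is unstratified, so no covariate is owed to the design. Adjusting for the baseline of the outcome is sound, the sample size assumes no covariates, and Protocol 7.2 calls the trial exploratory with descriptive p-values. All of that stands. A reader might infer that the planned analysis is flawed, or that its standard errors are demonstrably too large. The documents support neither inference, because they give no NTB reliability, residual SD or correlation between these tests.

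The likely gain is also limited. The single baseline is already an average of nine tests, six of them memory tests that overlap with the FCSRT. MMSE is restricted to 24 or higher, and FCSRT is truncated except in patients who qualify on the back-up test. ADAS-Cog11 at Visit 3 is given in the same battery as the NTB, so the two may share that day's error. These points pull the gain towards the low end. They also argue against adding three scores by default, since three cost more to estimate and the weakest two are the truncated ones.

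These points do not defeat the narrower change. ADAS-Cog11 has no entry cut-off in Protocol 3.3.2, and its Visit 1 score comes from a separate occasion. Part of the SAP contents after 7.4.1 is redacted and could hold supplementary adjusted analyses, but the primary model is fully visible and would be unaffected.

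**Conclusion.** The point holds as an optional efficiency improvement, not as an error. The planned analysis and the stated power remain valid without it. Precision is probably forgone, but the amount is unknown. For d = 0.5 and 48 versus 96, the gain runs from about nil to 4.6 power points (80.2% to at most 84.8%); ADAS-Cog11 alone gives at most about 83.6% under the assumptions in step 5.

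The upper figures need substantial noise in the baseline NTB, a strong correlation of the added scores with stable cognition, and independent errors. The low end is the likelier outcome if range restriction or shared same-day error is material. More optimistic inputs can be chosen: NTB reliability of 0.70 with three scores, each correlated 0.7 with cognition and with independent errors, gives g of about 18%. The entry cut-offs and the overlap between tests make that a poor basis for planning.

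**What to change.** Before unblinding, amend Protocol 7.3.1 and SAP 7.4.1 and 9.3 as follows.

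- Add pre-treatment ADAS-Cog11 as a continuous covariate, with its visit interaction, to the primary NTB MMRM. Use the Visit 1 score, or the mean of Visits 1 and 3, to limit error shared with the Visit 3 NTB.
- Use the same model for the Step 1 and Step 3 contrasts.
- Treat FCSRT free recall and MMSE as optional, because the entry cut-offs truncate them.
- Replace a missing covariate value with its overall baseline mean.
- Keep the model with baseline NTB alone as a sensitivity analysis.

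The MODEL statement in SAP 9.3 needs an edit in any case: it lists baseline twice and omits the baseline-by-visit term that Protocol 7.3.1 requires. Both changes can be made together. The cost is SAP wording and a few degrees of freedom, with no new data, visits or patients.
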